3 INVESTIGATIONAL PLAN

This is a multi-center, double-blind, randomized, placebo-controlled, dose-response clinical study investigating the efficacy and safety of *Rapamycin cream, topical* in the treatment of facial angiofibroma in patients with a diagnosis of TSC according to the clinical diagnostic criteria of International Tuberous Sclerosis Complex Consensus Conference 2012.

The study can be divided into a Screening Phase, a Treatment Phase, and Follow-Up (Figure 1).

[figure not shown]
During the Screening Phase, Informed Consent will be obtained for participants prior to the initiation of any study-specific procedures including eligibility confirmation. Following enrolment, up to two weeks prior to the first application of the study drug, participants will be randomly assigned to one of three possible treatments in a 1:1:1 ratio:

- *Rapamycin cream, topical* (0.5% rapamycin)
- *Rapamycin cream, topical* (1.0% rapamycin)
- Placebo cream

The Treatment Phase is divided into baseline visit (V0) and 5 subsequent clinical visits (V1-5).

Follow-up will be performed 28 days after V5 or the last visit where early withdrawal from treatment was confirmed.

Figure 1: Schematic of Trial Design

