10.2 Sample Size

This is the first randomized clinical trial of *Rapamycin cream, topical* applied to patients and the first time that the Investigator's Global Assessment (IGA) scale will be used for the assessment of the severity of facial angiofibroma.

It is anticipated that no more than 10% of the placebo group will achieve the primary endpoint, a successful treatment according to IGA scale after 26 weeks treatment and that each dose of *Rapamycin cream, topical* will achieve at least 40% successful treatment (42). Including the Holm-Bonferroni adjustment of the type I error rate for multiple comparisons ($\alpha = 0.025$), a sample size of 40 participants is required in each randomized group to achieve >80% power for these comparisons.

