10.3 Statistical Analyses

10.3.1 Primary Efficacy Endpoint

The data for the primary endpoint, the percentage of patients obtaining successful treatment based on the blind assessment using the IGA scale after 26 weeks or at last visit if early withdrawal/discontinuation, will be summarized by treatment group. Success is defined as clear or almost clear with an improvement of at least two grades from baseline, i.e. 2 to 0; 3 to 1. Statistical analysis of the primary endpoint will be performed using a logistic regression model which will include treatment effect and stratum as fixed factors and baseline IGA score as a covariate. This model will be used to generate the odds ratios and 95% confidence intervals of the individual dose treatments compared with placebo, with the p-values for these comparisons adjusted using the Holm-Bonferroni adjustment.

An exploratory analysis will compare the two active groups in the same manner as the primary endpoint, with no adjustment for multiple comparisons. This analysis will be summarized with the Odds ratio and 95% confidence interval.

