10.3.2 Secondary Efficacy Endpoints

The time-to-treatment success will be summarized using Kaplan-Meier analyses and compared between each dose group and placebo using the stratified log-rank test. The secondary endpoints change in IGA and FASI from baseline to 26 weeks/last assessment, and objective and subject improvement from baseline to 26 weeks/last assessment, will be summarized by treatment group using means, medians, standard deviations, interquartile ranges and minima and maxima. These changes will be analyzed using ANOVA including treatment and stratum as main effect fixed factors, with planned pairwise comparisons between each dose group and placebo. If the data is not adequately normally distributed the Kruskal-Wallis non-parametric ANOVA, and Mann-Whitney U tests comparing changes between treatment groups will be used for the analysis. Baseline for the IGA and FASI scores is defined as the last pre-treatment assessment, whether obtained at screening, randomization or V0.

Categorical Improvement scores will be compared amongst study groups using the Kruskal-Wallis non-parametric ANOVA, and Mann-Whitney U tests comparing changes between each dose group and placebo.

The type I error rate associated with the testing of the six secondary endpoints will be strictly controlled using the Hochberg procedure. This will involve ranking the 6 p-values derived from the testing of each dose group with placebo from highest to lowest. If the highest p-value is <0.05 , then all six comparisons are considered statistically significant if not significant then the next highest is tested at $p=0.025$. The p-value continues to reduce at each non-significant step based on the Bonferroni adjustment.

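### Nothing ties the secondary tests to the primary result, so a dose that fails its primary comparison can still be declared significant on a secondary endpoint, and study-wide error control is not specified

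*Combined protocol and SAP*

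**What the plan says.** **Primary family.** Section 10.3.1 compares each dose with placebo by logistic regression, "with the p-values for these comparisons adjusted using the Holm-Bonferroni adjustment". Section 10.2 sizes the trial at 0.025 per comparison, which is the first Holm step: "Including the Holm-Bonferroni adjustment of the type I error rate for multiple comparisons".

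**Secondary family.** Section 10.3.2 says "The type I error rate associated with the testing of the six secondary endpoints will be strictly controlled using the Hochberg procedure". The largest p-value is compared with 0.05, the next with 0.025, and so on down. The synopsis gives the same rule. Both places speak of six p-values, although six endpoints by two doses make 12 comparisons. The text can be read as one family or as one family of six per dose.

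**Link between the two.** Sections 10.1 to 10.6 and the synopsis contain no gate, hierarchy or alpha split. Section 10.3.3 suppresses p-values for the exploratory endpoints, so the plan does separate formal from descriptive results, and it places the secondaries on the formal side.

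**The concern.** Holm already spends 0.05 on the two primary comparisons. Hochberg then begins again at 0.05 whatever the primary showed. A dose could miss its primary comparison and still be reported as significant on a secondary, under wording that promises strict control.

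This is a plausible outcome here. The primary requires clear or almost clear skin plus a gain of two IGA grades, so a patient who starts at grade 2 must reach 0. The secondaries on IGA change, FASI change and percentage improvement have no such threshold. In a trial labelled Phase 2/3, a missed primary beside a formally significant secondary would be hard to interpret, and the plan gives no rule for it.

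**Working it through.** **1. The plan's own figure.** Inputs from section 10.2: 10% against 40% success, alpha 0.025, 80% power. Sidedness is not stated in words. Two-sided is assumed, because section 10.3.1 reports "odds ratios and 95% confidence intervals of the individual dose treatments compared with placebo". With a mean rate of 0.25:

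n = [z(0.9875)·√(2·0.25·0.75) + z(0.80)·√(0.1·0.9 + 0.4·0.6)]² / 0.30² = [2.241·0.612 + 0.842·0.574]² / 0.09 ≈ 38.3, so 39 per group.

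At 40 per group the power is 82%. This agrees with "a sample size of 40 participants is required in each randomized group to achieve >80% power for these comparisons" and confirms that the primary family uses 2 × 0.025 = 0.05.

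**2. Bounds, free of any correlation assumption between the families.**
- One secondary family: 0.05 + 0.05 = 10% (1 − 0.95² = 9.75% if the families were independent).
- One secondary family per dose: 0.05 + 0.05 + 0.05 = 15% (1 − 0.95³ = 14.3%).

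**3. Simulation with no effect anywhere.** Each of 400,000 trials has two primary and 12 secondary normal test statistics, tested two-sided. Section 3 says "participants will be randomly assigned to one of three possible treatments in a 1:1:1 ratio", so the two dose contrasts share a placebo group and correlate at 0.5. The correlation between endpoints is assumed and varied. Repeat runs differ by about 0.2 points.

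| Assumed endpoint correlation | 0 | 0.3 | 0.5 | 0.7 | 0.9 |
|---|---|---|---|---|---|
| Any false claim, one family of 12 | 9.2% | 8.6% | 7.8% | 6.6% | 5.1% |
| Any false claim, six tests per dose | 13.4% | 12.4% | 10.9% | 8.9% | 6.3% |
| Secondary claim for a dose that failed its primary, one family of 12 | 4.6% | 4.2% | 3.3% | 2.0% | 0.4% |

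The first two rows include the primary family's own error of about 4.7%. With six tests per dose, the quantity in the third row runs from 8.9% at correlation 0 to 4.4% at 0.7.

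**4. Candidate gates.** Every gate below gives about 4.7% when nothing works. The harder case is one dose that truly works on the primary and on nothing else:

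| Rule | Study-wide rate | Correlations run |
|---|---|---|
| No gate, one family of 12 | 7.2-9.0% | 0.7 to 0.3 |
| No gate, six per dose at 0.05 | 9.5-12.8% | 0.7 to 0.3 |
| Per-dose gate, Holm kept, each dose's six at 0.05 | 7.9-9.3% | 0.7 to 0.3 |
| Per-dose gate, Holm kept, one family of 12 with unopened endpoints set to p = 1 | 5.8-7.4% | 0.9 to 0 |
| Per-dose gate, Holm kept, each dose's six at 0.025 | 5.9-7.4% | 0.9 to 0 |
| One family of 12, opened only if both doses pass Holm | 5.0% within simulation error | all run |
| Plain 0.025 per dose on the primary, then that dose's six at 0.025 | at most 4.8% | 0.7 to 0.3 |

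**5. Why the last two hold.** With the both-doses gate, if either primary null is true, a false secondary claim requires that null to be falsely rejected first, and Holm already counts that within 5%. If neither is true, only Hochberg's own 5% remains. With 0.025 per dose, each dose's chain errs at most 2.5%, and 0.025 + 0.025 = 0.05.

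A per-dose gate that keeps Holm fails because the working dose opens its own secondaries and also releases the other dose's primary to the full 0.05. With the secondaries costing about 0.025, the sum is 0.05 + 0.025 = 7.5%, close to the 7.4% simulated.

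**The case against.** **The plan never promises 5% across both families.** A reader might infer that it claims 5% study-wide and breaks that claim. The documents do not support this. Section 10.3.1 covers the primary and section 10.3.2 covers the secondaries, each on its own. With one family of 12 the narrower promise is kept: the secondary family alone errs 2.1-4.8% when nothing works. Whether control within each family is enough is partly convention, and the documents cite no requirement for study-wide control and no labelling claim on secondaries. This objection stands, and it limits the criticism to control that is absent, not control that is broken.

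**The size depends on assumptions.** A reader might take 7-9% as the trial's error rate. That range needs one family of 12 and correlations of roughly 0.3 to 0.6, and the documents state neither. High correlation is plausible for some endpoints: time to success and IGA change come from the same IGA scores as the primary, and the other four rate the same lesions. At 0.9 the excess nearly vanishes. With six tests per dose, on the other hand, 7-9% is too low for most of the range. This also stands, so the bounds should lead and the simulated rates should be shown as a range.

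**The specific harm is smaller than the total.** With one family of 12, a secondary claim for a dose that failed its primary arises in 0.4-4.6% of null trials. That is correct. It does not answer the structural point, which needs no simulation: the written procedure permits such a claim.

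**Conclusion.** The concern holds in this form: the plan has neither a link nor an alpha split between the Holm family and the Hochberg family, so a secondary can be declared significant for a dose that failed the primary, and study-wide error control is not specified.

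The study-wide false-claim rate is at most 10% with one secondary family and 15% with one per dose. With no effect and assumed correlations from 0.9 to 0, it is about 5-9% or 6-13% respectively. These figures rest on two-sided tests, normal statistics and a common correlation among endpoints. A discrete primary test at low success rates would lower them slightly. The number of p-values in the Hochberg family affects both the size and the remedy, so it has to be settled at the same time. The primary analysis and its conclusion are not affected. Label: cheap improvement.

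**What to change.** Amend section 10.3.2 and the synopsis in one of two ways.

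- **Preferred.** Define one Hochberg family of 12 comparisons (six endpoints by two doses) at 0.05, tested formally only if both doses are rejected on the primary under Holm. Otherwise report the secondaries as estimates with confidence intervals. Cost: no formal secondary claim for a dose that succeeds alone.
- **If dose-specific secondary claims are wanted.** Test each dose's primary at a fixed 0.025, without Holm's step up to 0.05. Test that dose's six secondaries by Hochberg at 0.025 only if its primary p is below 0.025. Section 10.3.1 must then change too. Cost: a slightly stricter primary threshold for the second dose, although 0.025 is already the level used for the sample size. A graphical procedure with pre-stated weights would also serve.

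A per-dose gate that keeps Holm, with one 0.05 Hochberg family in which unopened endpoints count as p = 1, is better than no gate. It still leaves about 6-7% when one dose works on the primary only, and more if each dose's six are tested at 0.05.

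Either option takes a few sentences and needs no new data, visits or patients.

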	
the blind assessment using the IGA scale, will be summarized by treatment group. Success is defined as clear or almost clear with an improvement of at least two grades from baseline, i.e. 2 to 0; 3 to 1. Statistical analysis of the primary endpoint will be performed using a logistic regression model which will include treatment effect and stratum as fixed factors and baseline IGA score as a covariate. This model will be used to generate the odds ratios and 95% confidence intervals of the individual dose treatments compared with placebo, with the p-values for these comparisons adjusted using the Holm-Bonferroni adjustment.
 
Secondary Endpoints: The time-to-treatment success will be summarized using Kaplan-Meier analyses and compared between each dose group and placebo using the stratified log-rank test. The secondary endpoints change in IGA and FASI from baseline to 26 weeks/last assessment, and objective and subject improvement from baseline to 26 weeks/last assessment, will be summarized by treatment group using means, medians, standard deviations, interquartile ranges and minima and maxima. These changes will be analyzed using ANOVA including treatment and stratum as main effect fixed factors, with planned pairwise comparisons between each dose group and placebo. If the data is not adequately normally distributed the Kruskal-Wallis non-parametric ANOVA, and Mann-Whitney U tests comparing changes between treatment groups will be used for the analysis. Baseline for the IGA and FASI scores is defined as the last pre-treatment assessment, whether obtained at screening, randomization or V0.
 
Categorical Improvement scores will be compared amongst study groups using the Kruskal-Wallis non-parametric ANOVA, and Mann-Whitney U tests comparing changes between each dose group and placebo.
 
The type I error rate associated with the testing of the six secondary endpoints will be strictly controlled using the Hochberg procedure. This will involve ranking the 6 p-values derived from the testing of each dose group with placebo from highest to lowest. If the highest p-value is <0.05, then all six comparisons are considered statistically significant. If not significant then the next highest is tested at p=0.025. The p-value continues to reduce at each non-significant step based on the Bonferroni adjustment.
 
Exploratory Endpoints: The exploratory endpoints, including the change in IGA and FASI from week 26 to follow-up, will be analyzed in the same manner as the appropriate secondary endpoints. The p-values for these comparisons will not be reported but the differences between each dose group and placebo will be summarized as odds ratios or mean differences as appropriate with 95% confidence intervals.
 
Safety Endpoints: Safety Endpoints: AEs will be collected for all randomized participants and will be listed with type of AE, severity and relationship for each treatment group, using the safety population. Adverse event data will be summarized for each treatment groups using frequencies and percentages (% of participants with each specific AE). If frequencies permit, Chi-square tests or fisher's exact tests may be used to compare the rates of occurrence between treatment groups. Known AEs specific to oral or topical rapamycin will be individually summarized by treatment group.
 
Between-treatment comparisons will be made for changes in vital signs, hematology, biochemistry, blood lipids and urinalysis from baseline at visits V1-5. Baseline is defined as the last pre-treatment assessment, whether obtained at screening, randomization or V0. Changes between V5 and Follow-up will also be examined.
 
Blood rapamycin concentrations will be summarized for each of the treatment groups at all scheduled timepoints using standard descriptive statistics (means, medians, geometric means, ranges, standard deviations and standard errors), as appropriate.
 
Adverse events will be monitored up to 4 weeks after administration of the final dose of study medication.

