2.2 Efficacy Objectives

The Efficacy Objectives of the study are to determine and compare the efficacy of two different strengths of *Rapamycin cream, topical* and placebo over 26 weeks of once-daily treatment.

The primary efficacy endpoint is the percentage of patients obtaining successful treatment after 26 weeks or at discontinuation/withdrawal, based on the blind assessment using the IGA scale. Success is defined as clear or almost clear with an improvement of at least two grades from baseline, i.e. 2 to 0; 3 to 1.

The secondary efficacy endpoints are:

1. Time to treatment success
2. Change from baseline in IGA after 26 weeks treatment or at last visit if early withdrawal/discontinuation
3. Change from baseline in FASI after 26 weeks treatment or at last visit if early withdrawal/discontinuation
4. Subjective (patient or parent/caregiver) improvement rating from first visit (V0) after 26 weeks treatment or at last visit if early withdrawal/discontinuation
5. Objective (clinician) improvement rating from first visit (V0) after 26 weeks treatment or at last visit if early withdrawal/discontinuation
6. Categorical Improvement of Facial Angiofibroma from first visit (V0) after 26 weeks treatment

In addition, exploratory efficacy endpoints are:

1. The percentage of patients with successful treatment according to IGA scale after 2, 8, 14 and 20 weeks treatment
2. Change from baseline in IGA after 2, 8, 14 and 20 weeks treatment
3. Change from baseline in FASI after 2, 8, 14 and 20 weeks treatment
4. Change from baseline in each FASI component (erythema, size, extension) after 2, 8, 14, 20 and 26 weeks treatment
5. Subjective (patient or parent/caregiver) improvement rating from first visit (V0) after 2, 8, 14 and 20 weeks treatment
6. Objective (clinician) improvement rating from first visit (V0) after 2, 8, 14 and 20 weeks treatment
7. Change in IGA from week 26 to Follow up (4 weeks after final dose)

8. Change in FASI from week 26 to Follow up (4 weeks after final dose)

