6.1.2 Secondary and Exploratory Efficacy Endpoints

The following *secondary* efficacy endpoints will be derived from IGA scores:

1. Time to treatment success
2. Change from baseline in IGA after 26 weeks treatment or at last visit if early withdrawal/discontinuation

In addition, the following *exploratory* efficacy endpoint will be derived from IGA scores:

1. The percentage of patients with successful treatment according to IGA scale after 2, 8, 14 and 20 weeks treatment
2. Change from baseline in IGA after 2, 8, 14 and 20 weeks treatment
7. Change in IGA from week 26 to Follow-up (4 weeks after final dose)

Lesion severity will also be graded using the Facial Angiofibroma Severity Index (FASI) [Appendix 2: Facial Angiofibroma severity index (FASI)]. Using the FASI, lesions are graded according to their erythema, size and extent. Erythema is scored from 0 to 3 and lesion size are scored from 0 to 3, while extent carries greater specific weight (scored from 2 to 3), as the scale's developers consider the lesion's extent to be a fundamental factor in estimating the degree of severity.

The FASI is obtained by summing the partial scores assigned to each of three relevant features of FA for a maximum score of 9. FASI was first described in a clinical trial of 9 months duration (33) and the reliability and validity was subsequently reported (16). This will provide data for the following *secondary* efficacy endpoint:

3. The change in FASI from baseline after 26 weeks treatment or at last visit if early withdrawal/discontinuation

In addition, the following *exploratory* efficacy endpoints will be derived from FASI scores:

3. Change from baseline in FASI after 2, 8, 14 and 20 weeks treatment
4. Change from baseline in each FASI component (erythema, size, extension) after 2, 8, 14, 20 and 26 weeks treatment
8. Change in FASI from week 26 to Follow-up (4 weeks after final dose)

To the extent possible, the same Investigator should conduct all FASI assessments per patient at each site throughout the study.

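### The secondary Hochberg rule ranks 6 p-values where the plan generates 12, with no adjustment for two doses; run per dose, familywise error can reach about 9%

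*Combined protocol and SAP*

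**What the plan says.** Section 2.2 numbers six secondary endpoints: time to success, change in IGA, change in FASI, the subjective rating, the objective rating, and finally "Categorical Improvement of Facial Angiofibroma from first visit (V0) after 26 weeks treatment".

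Section 10.3.2 compares each dose with placebo on all six. Time to success uses a stratified log-rank test. The two change scores and the two ratings use ANOVA "with planned pairwise comparisons between each dose group and placebo", with a rank-test fallback. Categorical improvement uses Mann-Whitney tests of each dose against placebo.

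On multiplicity the same section states: "The type I error rate associated with the testing of the six secondary endpoints will be strictly controlled using the Hochberg procedure". It continues: "This will involve ranking the 6 p-values derived from the testing of each dose group with placebo from highest to lowest". If the largest p-value is below 0.05, "then all six comparisons are considered statistically significant". Otherwise the next is tested at 0.025, and so on down. The Statistical Methods part of the synopsis repeats the rule.

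For the primary endpoint, section 10.3.1 compares each dose with placebo "with the p-values for these comparisons adjusted using the Holm-Bonferroni adjustment". The sample size in section 10.2 uses the same correction: "Including the Holm-Bonferroni adjustment of the type I error rate for multiple comparisons", at 0.025.

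**The concern.** The rule does not fit the set of tests it is meant to govern. Six endpoints at two doses give 12 comparisons, but the rule counts six. The p-values are said to come from dose-against-placebo testing, so the three-group omnibus tests cannot be the missing six.

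Nothing says how 12 becomes six, whether the procedure runs once or twice, or how alpha is shared between the doses. No section makes secondary testing conditional on the primary result. Such a gate would not help in any case when both doses succeed on the primary.

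Two things are at stake. First, the promise of strict control may be untrue over the trial as a whole. Second, an undefined family leaves a choice to be made after unblinding, and that choice can decide which secondary results are called significant.

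**Working it through.** **Inputs from the documents.** Six secondary endpoints (2.2). Two dose-placebo comparisons per endpoint (10.3.2). Thresholds 0.05, 0.025, then 0.05/k (10.3.2). Allocation 1:1:1 with a shared placebo group (5.3).

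**Assumptions.** Tests are two-sided, since sidedness is not stated but 95% intervals are reported. Test statistics are approximately normal. Endpoints are equally correlated, and the correlation is varied because the documents give none.

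**The plan's own figures.** The plan gives no error rate for the secondary family. Its nearby computed figure does reproduce: 10% against 40% with 40 per group at two-sided alpha 0.025 gives 82.0% power, consistent with the stated figure of more than 80%.

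**Count.** 6 × 2 = 12 p-values, against 6 ranked. The rule's last threshold is 0.05/6 = 0.0083. A family of 12 would end at 0.05/12 = 0.0042.

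**Correlation between the two dose comparisons.** With equal arms of size n, Z_d = (mean_d − mean_P)/(σ√(2/n)). The shared placebo mean gives a correlation of (σ²/n)/(2σ²/n) = 0.5.

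**Exact case, one procedure per dose at 0.05.** Suppose one endpoint is truly null at both doses and the other five are so effective that they always pass. The null endpoint is then tested at the full 0.05 in each dose:

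- Error = 1 − P(|Z1| < 1.96, |Z2| < 1.96), correlation 0.5, = 0.0907.
- For reference, independent doses would give 1 − 0.95² = 0.0975, and the Bonferroni bound is 0.10.
- At 0.025 per dose the same formula gives 0.0465.

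**Simulation, all nulls true (1,000,000 trials), chance of at least one false claim:**

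| Endpoint correlation | Six tests per dose at 0.05 | One family of 12 | Six tests per dose at 0.025 |
|---|---|---|---|
| 0 | 9.1% | 4.7% | 4.7% |
| 0.3 | 8.7% | 4.5% | 4.5% |
| 0.5 | 7.7% | 4.1% | 4.1% |
| 0.7 | 6.3% | 3.3% | 3.4% |
| 0.9 | 4.5% | 2.2% | 2.4% |
| 1.0 | 9.1% | 1.9% | 4.7% |

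A separate run gave 5.4% at correlation 0.8 for the first column. Within a single dose the error stayed at about 5% or below throughout.

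**Simulation, one null and five effective endpoints per dose, six tests per dose at 0.05:**

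| Noncentrality of the five | Error over both doses |
|---|---|
| 8 | 9.1–9.2% at any correlation |
| 4 | 6.2–8.6% |
| 3 | 5.3–6.1% |
| 2 | 2.6–5.3% |

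**Other readings of the rule.** Ranking the smaller of the two dose p-values for each endpoint also gives about 9.1% under the global null with independent endpoints. Ranking all 12 in a proper 12-test procedure holds 5% but contradicts the stated count of six. Ranking 12 with the divisor stopping at six gives 9.1% at correlation 0 and 4.0% at 0.9 under the global null, but it too contradicts the stated count.

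**The case against.** The strongest reply has three parts.

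**The documented defect is an undefined family, and the inflation depends on how it is read.** If the statistician pooled all 12 p-values, error would be controlled and only the count would be wrong. This is correct, and the 9% is stated here only for the per-dose reading. But that reading fits the count of six, and pooling does not. On either reading the text has to change.

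**Taking each dose as its own family is defensible.** The promise refers to the six endpoints, and within a dose it is kept. This stands as a possible design choice. The plan does not state it, however, and the primary analysis takes the opposite view by adjusting across doses.

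**About 9% is the top of the range.** All six endpoints rate the same facial lesions, and for two of them section 6.1.2 says the "efficacy endpoints will be derived from IGA scores", so independence is unlikely. The plan's own primary effect implies a noncentrality of 0.30/√((0.1×0.9 + 0.4×0.6)/40) = 3.3. Applying that to five secondaries with one null gives 7.2%, 6.4% and 5.4% at correlations 0, 0.5 and 0.9. This is a fair limit on the likely size. It does not remove the excess, and larger effects on the continuous endpoints would move the error back towards 9%.

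**Conclusion.** The concern holds. The mismatch of 12 comparisons against six ranked p-values is on the page in both section 10.3.2 and the synopsis, and the secondary tests have no stated adjustment for two doses.

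On the per-dose reading, error over both doses is at most about 9.1% (exact 9.07% in the limiting case). For moderately to strongly correlated endpoints it is more plausibly between about 5% and 8%. It can fall below 5%, at very high correlation under the global null or when the other effects are weak.

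These sizes rest on the per-dose reading, two-sided tests, approximate normality and assumed correlations. The count does not depend on any of them. The primary test and the sample size are unaffected; only secondary claims are at stake. It should be fixed before unblinding.

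**What to change.** State the family in section 10.3.2 and in the synopsis, and make the counts agree with it. Either option works:

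- **One family of 12.** Rank all dose-by-endpoint p-values in one Hochberg procedure, with thresholds 0.05, 0.025, … 0.05/12 = 0.0042. Both counts of six become 12.
- **One family per dose at half alpha.** Run a six-test Hochberg procedure within each dose, with thresholds 0.025, 0.0125, … 0.025/6 = 0.0042. The text should refer to the six p-values for that dose.

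The largest error found was about 4.9% for the first and 4.7–4.8% for the second. If control within each dose is all that is intended, the plan should say so and withdraw the unqualified claim of strict control.

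Data collection and the primary analysis do not change. The cost is power on the secondary tests. At noncentrality 3.3, moving a single test from 0.05 to 0.025 lowers power from about 91% to 86%, and from 0.0083 to 0.0042 from about 75% to 67%. The first option keeps the opening step at 0.05, which helps if both doses are expected to work on every endpoint. The second keeps a failure at one dose from affecting the other.
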